8.5 Concomitant Medications and Supportive Care

The following medications and interventions, unless otherwise specified, are prohibited from the time of study screening until the End of Treatment visit:

- Anti-cancer therapy, including chemotherapy, radiotherapy, or endocrine therapy other than those required per protocol.
- Any investigational drug or device other than Vigil.
- Systemic—oral, IV, injectable—corticosteroids (e.g., dexamethasone) should be avoided in subjects who are administered Vigil. If deemed by the investigator to be necessary, short term (<30 days) systemic steroids ≤ 0.25 mg/kg (max 10mg) prednisone-equivalent per day and inhaled steroids are permitted while on protocol. Other steroid regimens and/or immunosuppressives are generally prohibited. Contact the Gradalis medical monitor if other steroidal regimens are clinically needed.
- Localized radiotherapy is permitted for palliation of painful lesions at the investigator's discretion. However, medical management in place of radiation therapy should be used, if clinically appropriate. Inactivated vaccines are allowed on study, if deemed appropriate by the investigator. Live vaccines are prohibited while on study.
- Valproic Acid (due to temozolomide)
- Strong CYP34A inducers and inhibitors (due to irinotecan)

Subjects should be provided with full supportive care measures, as clinically indicated, and in accordance with institutional standards. Such care includes medication for pain control and symptom management, antibiotics, bisphosphonates, antiemetics, colony stimulating factors, and transfusions of blood or blood products. Prophylactic GCSF is allowed for both treatment arms, if indicated. Treatment for drug-related adverse events should be administered at the discretion of the investigator.

Peg-filgrastim may be administered after completion of Day 5 temozolomide to facilitate ANC recovery.

8.6 Contraception

Female subjects of childbearing potential must consent to use a medically acceptable method of highly effective contraception (oral hormonal contraceptive, condom plus spermicide, or hormone implants) throughout the study period and for 28 days after their final autologous Vigil administration. A method of contraception must be employed by all subjects (male and female).

8.7 Toxicity

Toxicities will be graded and reported according to the NCI Common Toxicity Criteria for Adverse Events (CTCAE) Version 5. This document can also be downloaded from the Cancer Therapy Evaluation Program (CTEP) home page http://ctep.cancer.gov>.

Adverse events will be summarized using the MedDRA coding system or higher. The NCI-CTCAE will be used for AE grading. All AEs, regardless of severity, will be followed by the Treating Physician until resolution is satisfactory.

9.0 SCHEDULE OF ASSESSMENTS

Pre-study Assessments / Surgery Pre-Screening

The following evaluations will be performed within 4 weeks of tumor procurement (unless otherwise specified):

- 1. A signed Informed Consent Form for tissue harvest must be obtained.
- 2. It has been confirmed that the subject meets all tissue procurement inclusion criteria and none of the exclusion criteria.
- 3. A complete medical history must be obtained.
- 4. A physical examination must be obtained.

- 5. A complete blood count (CBC) with differential and platelet count must be performed. (HIV and hepatitis testing is not required if the subject has no medical history of HIV).
- 6. Routine pre-operative serum chemistries (including, but not limited to creatinine, total bilirubin, alkaline phosphatase, and aspartate transaminase (AST) and/or alanine transaminase (ALT).
- 7. Blood collection for immune function analysis will be obtained at tissue harvest. (≤1 week of tissue procurement)
- 8. Plasma collection for immune function analysis (ctDNA) (≤1 week of tissue procurement)

Screening Assessments / Protocol Screening

The following evaluations will be performed on all subjects within 2 weeks of Cycle 1 (unless otherwise specified):

- 1. A signed protocol specific Informed Consent Form must be obtained.
- 2. It has been confirmed that the subject meets all inclusion criteria and none of the exclusion criteria.
- 3. A physical examination (including vital signs, height, temperature and body weight) must be obtained.
- 4. Assessment of concomitant medications
- 5. Assessment of PS on the Karnofsky or Lansky scale (see Appendix A) must be obtained.
- 6. Radiological assessment of disease status with computed tomography (CT) chest /abdomen/pelvis (magnetic resonance imaging (MRI) abd/pelvis may be substituted for CT abd/pelvis) within 4 weeks of Cycle 1. The methods used for prestudy assessments (e.g., CT or MRI) should be used throughout the study. If possible, the same equipment should be used each time. Radiographic assessments must be from after the tissue harvest for vaccine manufacture to ensure true baseline disease status is captured. Images must be uploaded into WorldPro or submitted to WorldCare.
- 7. A complete blood count (CBC) with differential and platelet count must be performed. (HIV and hepatitis testing is not required if the subject has no medical history of HIV).
- 8. Serum chemistries (creatinine, glucose, total protein, blood urea nitrogen (BUN), total carbon dioxide (CO2), albumin, total bilirubin, alkaline phosphatase, and aspartate transaminase (AST) and/or alanine transaminase (ALT)) and electrolytes (total calcium, chloride, potassium, sodium) must be performed.
- 9. Blood collection for immune function analysis (ELISPOT).
- 10. Plasma collection for immune function analysis (ctDNA).
- 11. Pregnancy test for those of childbearing potential.
- 12. Submission to Gradalis, Inc. of preferably 20 unstained tumor slides or tissue block for correlative immunohistochemistry assay. These slides should correlate with tumor procured for vaccine manufacture.

Assessments During Treatment

The following evaluations will be performed on Day 1 of each cycle (1 Cycle = 21 days \pm 3 days) (unless otherwise specified):

- 1. *A physical examination, including vital signs and body weight.
- 2. *A toxicity assessment (CTCAE v 5).
- 3. *Assessment of concomitant medications.
- 4. Radiological assessment of disease status with CT chest /abd/pelvis (MRI abd/pelvis may be substituted for CT abd/pelvis) every 6 weeks ± 7 days from Cycle 1 regardless of treatment arm assignment or treatment delay. The methods used for prestudy assessments (e.g., CT or MRI) should be used throughout the study. If possible, the same equipment should be used each time.
- 5. *A CBC with differential and platelet count.
- 6. *Serum chemistries (creatinine, glucose, total protein, blood urea nitrogen (BUN), total carbon dioxide (CO2), albumin, total bilirubin, alkaline phosphatase, and aspartate transaminase (AST) and/or alanine transaminase (ALT)) and electrolytes (total calcium, chloride, potassium, sodium).
- 7. Blood collection for immune function analysis (ELISPOT) on Day 1 (prior to chemotherapy administration) at Cycles 2, 4, and 6.
- 8. Plasma collection for immune function analysis (ctDNA) on Day 1 prior to chemotherapy administration at Cycles 2, 3, 4 and 6.
- 9. *Assessment of Karnofsky Performance Status or LS.
- 10. Group A and B participants: oral temozolomide 100 mg/m² daily (Days 1 5, total dose 500 mg/m²/cycle)
- 11. Group A and B participants: oral irinotecan 50 mg/m² daily (Days 1 5, total dose 250mg/m²/cycle)
- 12. Group A participants: Vigil 1.0 x 10⁶ cells/injection, intradermally on Day 15.
- 13. Cross-over Subjects: Vigil 1.0 x 10⁶ cells/injection, intradermally every 21 days
- 14. For those randomized to Group A or in cross-over, Vigil administration. Day 16 post Vigil administration assessment of injection site. Instruct the subject on Day 15 to observe the injection site 24 hours after the product administration. (This may be conducted at home). Have the subject follow up with the clinic if an injection site reaction is present. Please note if the subject reports of any redness, swelling or other response. If the subject identifies any redness, and /or swelling, please ask the subject if it is feasible to take a photograph of the injection site. If photographing the injection site is possible, please instruct the subject to place a measuring tool (bulk supplies provided to the site) next to the injection site reaction in the picture, if feasible. The photograph may be provided to the clinic upon the next visit as a hard copy or electronic jpg image. Please instruct the participant to avoid capturing images that would identify the subject (i.e. face and head).
- 15. Submission of Next Generation Sequencing data, if available in medical records.

Subjects who are stable at the end of Cycle 4, with prior approval by the Sponsor may conduct evaluations denoted with an asterisk* on Day 15 of each cycle (1 Cycle = 21 days \pm 3 days) (unless otherwise specified).

Subjects who become child-bearing while on study will have a pregnancy test performed prior to their next dose. See Section 8.6.

End of Treatment Assessments

The following evaluations will be performed within 30 days after completion of the study regimen and / or within 30 days of disease progression (whichever event occurs first) (unless otherwise specified):

- 1. A physical examination, including vital signs and body weight.
- 2. Toxicity assessment (adverse events).
- 3. Assessment of concomitant medications taken.
- 4. Assessment of Karnofsky Performance Status/Lansky Performance Status
- 5. Radiological assessment of disease status with CT chest /abd/pelvis (MRI abd/pelvis may be substituted for CT abd/pelvis) within 45 days of the last injection or disease recurrence or progression
- 6. A CBC with differential and platelet count.
- 7. Serum chemistries (creatinine, glucose, total protein, blood urea nitrogen (BUN), total carbon dioxide (CO2), albumin, total bilirubin, alkaline phosphatase, and aspartate transaminase (AST) and/or alanine transaminase (ALT)) and electrolytes (total calcium, chloride, potassium, sodium).
- 8. Blood (PBMC) for immune function analysis (ELISPOT).
- 9. Plasma for immune function analysis (ctDNA).

Response Follow Up Assessments

If the study agent is discontinued (for reasons such as completion of all available doses of vaccine, intolerable toxicity, treatment interruption of more than 4 weeks, intercurrent illness, protocol deviation, at PI's discretion), the subject will be followed quarterly after the end of study visit until progression.

The following evaluations will be performed quarterly (every 3 months ±7 days) (unless otherwise specified):

- 1. A physical examination, including vital signs and body weight.
- 2. Assessment of concomitant medications taken.
- Radiological assessment of disease status with CT chest /abd/pelvis (MRI abd/pelvis may be substituted for CT abd/pelvis) must be collected. The methods used for prestudy assessments (e.g., CT or MRI) should be used throughout the study. If possible, the same equipment should be used each time.
- 4. A CBC with differential and platelet count.

- 5. Serum chemistries (creatinine, glucose, total protein, blood urea nitrogen (BUN), total carbon dioxide (CO2), albumin, total bilirubin, alkaline phosphatase, and aspartate transaminase (AST) and/or alanine transaminase (ALT)) and electrolytes (total calcium, chloride, potassium, sodium).
- 6. Blood collection for immune function analysis (ELISPOT) 3 months ±7 days from EOT and every 6 months ±7 days thereafter.
- 7. Assessment of Performance Status.

Long Term Follow Up

After progression, subjects and their physicians will be contacted quarterly for documentation of post study therapies and survival status.

As the intent-to-treat population includes all randomized patients, should a subject be randomized and choose to not receive any treatment on this study, the subject should be asked if he or she is willing to allow for survival follow up through phone call and/or physician contact quarterly. This follow up would include any anti-cancer therapies received and survival status information.

Based on findings during the study or during the follow up portion of the trial, Gradalis may request for additional blood and / or tissue samples from the research participant. Collection of whole blood (40ml) and / or tissue samples (via biopsy or clinically indicated surgical removal) will be **optional** and used to study the effects of the study agent (included, but not limited to testing of biomarkers, predictors or biological responses, toxicity, relationship between genotype and study agent responses).

Should Gradalis request for additional blood or tissue and the subject consented to the collection, the clinical site will present the option of the procurement to the participant.

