6.4 Study Enrollment Inclusion Criteria

Subjects will be eligible for registration if they meet the tissue procurement inclusion criteria and all of the following study enrollment inclusion criteria:

- 1. Completed manufacture of at least 4 vials of Vigil.
- 2. Karnofsky performance status (KPS) / Lansky performance status (LS) ≥80%.
- 3. Normal organ and marrow function as defined below:

Absolute granulocyte count	≥1,000/mm³
Absolute lymphocyte count	≥400/mm³
Platelets	≥75,000/mm³
Hemoglobin	≥8.0 mg/dL
Total bilirubin	≤ institutional upper limit of normal*
AST(SGOT)/ALT(SGPT)	≤2x institutional upper limit of normal
Creatinine	<1.5 mg/dL

*documented Gilbert's syndrome may be considered after medical monitor review

- 4. Subject has recovered to CTCAE Grade 1 (except for parameters noted in Item 3, above) or better from all adverse events associated with prior therapy or surgery. Preexisting motor, sensory neurologic pathology or symptoms, or dermatologic must be recovered to CTCAE Grade 2 or better.
- 5. If female of childbearing potential, has a negative urine or serum pregnancy test. If the urine test is positive or cannot be confirmed as negative, a negative serum test will be required for study entry.
- 6. Ability to understand and the willingness to sign a written informed protocol specific consent or a parental/guardian informed consent and pediatric assent when appropriate.

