14.5 Serious Adverse Event Reporting

All SAEs will be reported to Gradalis, Inc. within 24 hours of notification by the site through email or facsimile. This includes any death from any cause following procurement of the subject's tissue for tissue manufacture and for up to 30 days following the last dose of the protocol study agent (Vigil).

The site will supply as much information as is available at the time of the initial notification (study number, patient initials, patient study number, onset date, relationship, patient demographics, event, dosing regimen of study agent) to:

Gradalis, Inc.			
[name]			
[contact]			
Direct: [contact]	[contact]		

Gradalis, Inc. will report adverse events to the FDA in compliance with 21 CFR 312.32.

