12.1.1 Radiology Tumor Assessment

Radiology tumor assessment will be performed within 4 weeks of the registration.

If the study agent is completed or discontinued before disease recurrence the subject will be followed for recurrence on the following schedule. Radiological assessment of disease status until disease recurrence (i.e., chest X-ray, (chest CT or MRI is acceptable), pelvic/abdominal CT or MRI) performed quarterly (every 3 months ±7 days). The methods used for prestudy assessments (e.g., CT or MRI) should be used throughout the study and if possible, the same equipment should be used each time.

Radiology tumor assessment will be summarized with descriptive statistics in a summary table. A detailed listing will be provided.

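### The documents conflict on when 6-weekly scans give way to quarterly ones, and one of the triggers, running out of vaccine, can arise only in Group A

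*Protocol*

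**What the plan says.** Protocol 9.0 contains two scan schedules.

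- **Assessments During Treatment:** scans are "every 6 weeks ± 7 days from Cycle 1 regardless of treatment arm assignment or treatment delay".
- **Response Follow Up Assessments:** the condition begins "If the study agent is discontinued (for reasons such as completion of all available doses of vaccine" and goes on to list intolerable toxicity, interruption of more than 4 weeks, intercurrent illness, protocol deviation and the investigator's discretion. Then "the subject will be followed quarterly after the end of study visit until progression", with a window of 3 months ±7 days.

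SAP 12.1.1 repeats the second rule: "If the study agent is completed or discontinued before disease recurrence the subject will be followed for recurrence", also quarterly.

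Protocol 14.5 equates the study agent with Vigil ("following the last dose of the protocol study agent (Vigil"). The Vigil transfer text in Protocol 8.4.1 uses the term in the same way. Protocol 7.1, however, speaks of study agents in the plural.

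The End of Treatment text in Protocol 9.0 ties the visit to completion of the study regimen or to progression, but times the scan from the last injection or from recurrence or progression. The Synopsis (Duration) lets cycles repeat until progression. Protocol 8.4.1 puts chemotherapy beyond 12 cycles off study in both arms.

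Entry requires "Completed manufacture of at least 4 vials of Vigil" (Protocol 6.4). The maximum is 12 doses, limited by what the patient's own tumour yields.

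**The concern.** Progression is dated at the scan that shows it, so a longer scan interval dates it later. Group B can receive vaccine only after cross-over, and Protocol 10.1 requires radiologic progression for that. Completing all vaccine doses can therefore move only Group A patients to quarterly scans before their PFS event.

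A Group A patient with 4 doses could make that move at about week 11, while a Group B patient on the same chemotherapy stays on 6-weekly scans. The trial is open label (Protocol 16.1), so a site choosing between the two rules would know the arm. None of the five PFS sensitivity analyses in Protocol 16.4.3 or SAP 8.1.3 deals with unequal scan intervals or interval censoring. At stake is a tilt in the primary endpoint toward the experimental arm.

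**Working it through.** **1. The plan's own figures.** Inputs from Protocol 16.1: HR 0.45, two-sided alpha 0.0476, power 90%, control median 6 months, 12 months' accrual, 6 months' follow-up.

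- Events (Schoenfeld): 4(1.981 + 1.282)² / (ln 0.45)² = 66.8, i.e. 67, as stated.
- Probability of an event under exponential PFS with uniform accrual: 1 − (e^(−6λ) − e^(−18λ))/(12λ), which is 0.729 in control and 0.455 in Vigil (mean 0.592).
- Patients: 67 / 0.592 = 113.1, i.e. 114 at 1:1, as stated.

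**2. When vaccine runs out.** One dose is given on Day 15 of each 21-day cycle. Dose 4 falls on day 3 × 21 + 15 = 78 (week 11) and dose 12 on day 11 × 21 + 15 = 246 (week 35). The 12-cycle limit is 252 days (week 36). With a 6-month median, the share of patients progression-free at the end of cycle 4 (day 84, about 2.76 months) is 2^(−2.76/6) = 0.73. Most patients would therefore still be at risk when a 4-dose switch occurs.

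**3. Which rule governs.** Consider a Group A patient out of vaccine but still on chemotherapy. The study-agent wording and SAP 12.1.1 point to quarterly scans. The on-treatment heading, the regimen-based End of Treatment visit and the Synopsis point to 6-weekly scans. Appendix B does not settle it.

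**4. Size if the vaccine trigger is applied.** I simulated the trial with no true effect:

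- 57 patients per arm, analysed at 67 detected events by log-rank at two-sided 0.0476, without the interim look;
- progression dated at the next scan, ±7 days' jitter, 91 days per quarter;
- censoring at the last scan;
- 4,000 runs per scenario, with a Monte Carlo error of 0.2 to 0.4 percentage points.

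The ranges cover an End of Treatment scan at the end of the last cycle or 0-30 days later. Error is the one-sided rate favouring Vigil (nominal 2.38%). The dose scenarios are assumptions.

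| Group A doses | Group B 6-weekly throughout | Group B quarterly after 12 cycles |
|---|---|---|
| all 4 | HR 0.92-0.97; 3.5-5.5% | HR 0.87-0.93; 4.8-7.6% |
| all 6 | HR 0.94-0.98; 2.9-4.1% | HR 0.98-1.00; 2.6-3.1% |
| all 8 | HR 0.95-0.99; 2.5-4.6% | not run |
| all 12 | HR 0.98-1.00; 2.8-3.2% | same schedule in both arms: HR 1.00-1.01; 1.9-2.0% |
| even over 4-12 | HR 0.97-0.98; 2.5-2.6% | HR 0.98-0.99; 2.9-3.2% |

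With both arms 6-weekly throughout, the result is HR 1.00 and 2.3-2.4%.

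With Group B 6-weekly, detected median PFS is 7.5-7.6 months in Group A against 6.8 in Group B when all have 4 doses, and 7.3 against 6.8 for doses over 4-12.

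**5. Sensitivity of these results.**

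- If 20% of events are deaths dated exactly (assumption), the 4-dose case with Group B 6-weekly falls to HR 0.98 and 3.1%.
- A separate run with 10% deaths and Group B quarterly after 12 cycles (2,000 trials) gave HR 0.94 and 4.2% for 4 doses, HR 0.97 and 2.9% for 4-12, and HR 1.00 and 2.6% on a common schedule.
- At a true HR of 0.45 (Group B 6-weekly) the observed HR is 0.435 (4 doses) or 0.443 (4-12), against 0.446 with equal schedules.
- The log-rank result depends on how the two scan grids line up. With no jitter at all, which is unrealistic, the 4-dose case reached HR 0.80-0.85 and 7.5-12%.

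**The case against.** A reader might infer that the plan dictates a switch in one arm and that PFS is therefore biased toward Vigil. The documents do not support that, for four reasons.

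1. **The trigger is not settled.** A patient still receiving chemotherapy cycles can fairly be called on treatment, where 6-weekly scanning applies regardless of arm. To say that this sentence does not govern such a patient assumes the point in dispute.
2. **The study agent may not mean Vigil alone here.** Protocol 10.0 provides for Group B patients who progress 8 weeks or more after End of Treatment. If the term covered only Vigil, those patients would have no scan schedule before progression.
3. **Quarterly scanning is not confined to Group A.** Vaccine exhaustion is, but the other listed reasons and the 12-cycle limit can bring Group B to it too.
4. **There is an opposite asymmetry.** When chemotherapy stops for toxicity, Protocol 7.1 and 8.4.1 allow Vigil to continue. Such a Group A patient may stay on 6-weekly scans while the Group B counterpart moves to quarterly. In a 1,500-run simulation (error about 0.4 points, stopping rates assumed) with doses spread over 4-12, the result went from HR 0.98 and 3.1% with no early stopping in Group B to HR 0.99 and 2.3% at 25% stopping and HR 1.00 and 2.5% at 50%. With all patients at 4 doses, the error fell from 5.1% to 4.1% and 3.8%.

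All four stand as limits on certainty and size. They do not remove the conflict between the rules, and the last shows only that its effect may be partly offset. It is also fair to say that an interval-censored analysis is a safeguard rather than the correction of an error.

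**Conclusion.** The point holds as a conflict with a possible bias. Protocol 9.0 and SAP 12.1.1 leave open when 6-weekly scanning ends. One written trigger can operate only in Group A, and no planned analysis would expose the result.

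If that trigger is applied, later detection in Group A tilts PFS toward Vigil. The tilt is material only if vaccine commonly runs out near the 4-dose minimum: HR 0.87-0.97 and 3.5-7.6% one-sided error, or HR 0.98 and 3.1% with 20% exactly dated deaths. For doses spread evenly over 4-12 it is small (HR 0.97-0.99, about 2.5-3.2%), and at 12 doses it is near zero. At the design HR of 0.45 it hardly matters. If both arms change schedule only after 12 cycles, there is no bias.

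These sizes rest on assumed dose counts, exponential PFS with a 6-month median, and a single final analysis. The change should be made because it is cheap and because scans not taken cannot be recovered later.

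**What to change.** Reconcile the three parts of Protocol 9.0 (During Treatment, End of Treatment, Response Follow Up), Appendix B and SAP 12.1.1 to one scan calendar. Count it from randomisation in both arms: 6-weekly to one stated week, then every 3 months until progression, regardless of arm, vaccine supply or chemotherapy status. Week 36 would be a natural choice, since 12 cycles × 3 weeks = 36 weeks. Scans would then no longer depend on what the study agent or the study regimen is taken to mean.

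Add an interval-censored PFS analysis to the sensitivity analyses in Protocol 16.4.3 and SAP 8.1.3.

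The cost is protocol and SAP wording, plus a few extra routine scans for patients in either arm who stop treatment early. The interval-censored analysis needs no extra scans.

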16.2 Definition of Progression Free Survival (PFS)

- Progression free survival (PFS) is defined as the time from randomization to the event of disease recurrence/progression or death due to any cause.
- Radiographic disease recurrence/progression will be assessed using the RECIST 1.1 criteria. If the disease recurrence/progression assessment involves more than one date, the earliest date will be used as the event date.
- Patients who are alive and recurrence free at the time of analysis data cut-off, or who terminate the study for reasons other than disease progression or death, or who receive non-protocol treatment for Ewing's Sarcoma, will be censored on the last assessment date at which a RECIST 1.1 evaluation of disease status was made.
- Patients missing baseline disease assessment will be censored at date of randomization.
- For equivocal findings of recurrence (e.g., very small and uncertain new lesions; cystic changes or necrosis in existing lesions), treatment may continue until the next scheduled assessment. If recurrence is confirmed at the next scheduled assessment, the date of recurrence should be the earlier date when recurrence was suspected.

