16.3 Analysis Populations

The intent-to-treat (ITT) population will include all randomized subjects. All efficacy analyses will be completed in the ITT population.

The Safety population will include all patients who receive study treatment and patients will be analyzed according to actual treatment received. All safety analyses will be completed in the Safety population.

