16.4.3 Sensitivity Analyses of the Primary Endpoint

Five sensitivity analyses of the primary endpoint will be conducted using each of the following modifications to the definition of PFS:

- If the disease recurrence/progression assessment involves more than one date, the latest date will be used as the event date.
- If disease recurrence or death occurs right after missing data for a scheduled radiographic disease assessment (including missing the assessment or assessment results in an unevaluable status for overall response per RECIST 1.1), the patient will be censored at the date of the last radiographic disease assessment.
- If a patient receives non-protocol treatment for Ewing's Sarcoma, the patient will be treated as having progression at the date of the last radiographic disease assessment.
- Patients missing baseline disease assessment will be treating as had having progression at the date of randomization.
- For equivocal findings of recurrence (e.g., very small and uncertain new lesions; cystic changes or necrosis in existing lesions) for whom treatment continues until the next scheduled assessment, and if recurrence is confirmed at the next scheduled assessment, the date of recurrence should be the date when recurrence was confirmed.

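### Subjects randomised but never treated stay in the ITT set, yet their progression is not collected, so primary PFS censors most of them at about day 0 and one sensitivity analysis can count them as progressed at about day 0

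*Protocol*

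**What the plan says.** **Who is meant.** Protocol 9.0, under Long Term Follow Up, covers the case "should a subject be randomized and choose to not receive any treatment on this study". It gives the ITT population as the reason for keeping contact.

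**What is collected.** "the subject should be asked if he or she is willing to allow for survival follow up through phone call and/or physician contact quarterly", and "This follow up would include any anti-cancer therapies received and survival status information". No imaging or progression date is requested.

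**Other schedules in 9.0.** On-treatment imaging runs "every 6 weeks ± 7 days from Cycle 1 regardless of treatment arm assignment or treatment delay". In Response Follow Up, once the study agent has been discontinued, "the subject will be followed quarterly after the end of study visit until progression". SAP 12.1.1 likewise starts post-treatment imaging when the study agent is completed or discontinued.

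**Analysis set.** Protocol 16.3 and SAP 8.0 define ITT as all randomised subjects: "All efficacy analyses will be completed in the ITT population".

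**Primary rule (Protocol 16.2, SAP 7.1).** Subjects who are alive and recurrence-free at cut-off, who leave the study for other reasons, or who receive non-protocol treatment "will be censored on the last assessment date at which a RECIST 1.1 evaluation of disease status was made". Without a baseline assessment, they are censored at randomisation. Death from any cause is an event. SAP 10.1.2 rules out imputation for the primary endpoint.

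**Third sensitivity analysis (Protocol 16.4.3, SAP 8.1.3).** The event is dated to the most recent scan: "If a patient receives non-protocol treatment for Ewing's Sarcoma, the patient will be treated as having progression at the date of the last radiographic" (quote cut just before its sentence ends).

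**The concern.** The protocol names these subjects because ITT requires them, then does not collect the main component of the primary endpoint for them. Neither scan schedule clearly reaches someone who never starts Cycle 1 and so never discontinues. The only study RECIST evaluation is then the screening scan. By 9.0 and 8.1 that scan normally precedes the randomisation result.

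Two things follow, in two different analyses. In primary PFS the subject usually leaves the risk set at or before day 0, so a comparison labelled ITT omits a group that may differ by arm. In the third sensitivity analysis, a subject who took another regimen becomes an event at or before day 0. The analysis that should test the censoring rule then adds immediate events to whichever arm had the refusals. None of the five sensitivity analyses counts actual progression regardless of the treatment taken.

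Unequal refusal is possible. The trial is open label, and at least four vials of the subject's own product exist before allocation to chemotherapy alone is disclosed.

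**Working it through.** **1. The plan's own figures (Protocol 16.1).** Inputs: HR 0.45, two-sided alpha 0.0476, power 90%, 1:1 allocation, control median 6 months, 12 months of accrual, 6 months of further follow-up.

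- Events (Schoenfeld): 4 × (1.981 + 1.282)² / (ln 0.45)² = 66.8, so 67.
- Event probability with exponential PFS and uniform accrual: 1 − (e^(−6λ) − e^(−18λ)) / (12λ). Control, λ = ln 2 / 6: 0.7295. Vigil, 0.45λ: 0.4554.
- N = 67 / ((0.7295 + 0.4554) / 2) = 113.1, so 114 when rounded up to an even number.

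Both figures reproduce, with no allowance for untreated subjects.

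**2. Loss of information.** Suppose 10% of Group B is censored at day 0. Expected events at month 18 are 57 × 0.9 × 0.7295 + 57 × 0.4554 = 37.4 + 26.0 = 63.4. Power is then about 88.4%. Waiting for 67 events takes about 7.2 months of follow-up instead of 6 and largely restores power. Power is therefore the minor issue; bias is the lasting one.

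**3. Bias under no true effect.** The documents give no refusal rate, so these inputs are assumptions: six of 57 (about 10%) decline; half of subjects have 0.6 times and half 1.6 times the control hazard; accrual is uniform over 12 months with cut-off at month 18. Primary: decliners are removed at day 0. Third sensitivity analysis: every decliner takes non-protocol treatment and is an event at day 0.

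| Who declines | Primary HR | Third sensitivity HR |
|---|---|---|
| Group B, better-prognosis half | 0.94 | 0.81 |
| Group B, unrelated to prognosis | 1.00 | 0.86 |
| Group B, worse-prognosis half | 1.06 | 0.91 |
| Group A, better-prognosis half | 1.06 | 1.22 |

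Repeat simulations agree to within about 0.01. Six unrelated decliners in each arm give a primary HR of 1.00. In the first row the primary test wrongly favours Vigil in about 4% of trials, against a nominal one-sided 2.4%.

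A separate model (analysis at 67 events, 15% of Group B declining) shows the same pattern. The primary HR is about 0.91 if decliners have half the hazard of the others and 1.10 if they have double. The corresponding day-0-event HRs are about 0.71 and 0.84.

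**4. Why the third analysis has a fixed direction for a given arm.** At day 0 there are 57 at risk in each arm. Six events, all in Group B, give Vigil 0 observed against 3 expected, so observed minus expected starts at −3.

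- Variance from the day-0 events: 6 × 0.25 × 108/113 = 1.4.
- Later events under no effect: 108 × 0.7295 = 78.8. Their variance is about 78.8 × (57/108) × (51/108) = 19.6.
- One-step log HR: −3 / 21.0 = −0.14, so HR is about 0.87.

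That is close to the simulated 0.86 and needs no assumption about prognosis. Prognosis only shifts the result around that value.

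**The case against.** **Refusal in Group B may be rare.** Protocol 10.0 lets Group B subjects receive their own Vigil after RECIST progression if they have had no alternative therapy since end of treatment, and 8.3 bars supply outside the protocol. Leaving for another regimen therefore forfeits the product. In the earlier randomised Ewing's trial (2.4), all eight control subjects received their chemotherapy and no control refusal is reported. This stands: the text does not show that refusal will be unequal, and the number could be zero.

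**The phase I share is not a refusal rate.** A reader might take the five of 30 subjects in 2.2 who chose other management (17%) as an anchor. They were in a non-randomised trial in which Vigil was the study treatment, so they say nothing about refusing a control arm.

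**Some outcomes are used.** A reader might infer that untreated subjects contribute to no planned analysis. That is too strong. ITT overall survival, next in the fixed sequence after PFS, uses exactly this follow-up. A subject who takes no other therapy and dies while in contact can be a PFS event under 16.2, although the sensitivity rule on missed assessments could censor that death.

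**The third sensitivity analysis decides nothing.** It is one of five and has no role in the decision rule, so its rejection rate is not a trial error rate. The figures also assume that every decliner takes other therapy and that a scan dated before randomisation is moved to day 0, a point on which the documents are silent.

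These points limit likelihood and size. They do not supply the missing progression data.

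**Conclusion.** The gap is real on the text: progression is not collected for randomised but untreated subjects, and the rules as written place them at about day 0. Censoring is the primary rule. Progression dated to the baseline scan applies only in the third sensitivity analysis, and only after non-protocol treatment.

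A reader might infer that primary PFS is biased towards Vigil. The documents do not support that. With an assumed 10% declining in Group B the primary HR under no effect runs from about 0.94 to 1.06, and it is 1.00 if refusal is unrelated to prognosis. The third sensitivity analysis does have a direction, set by the arm that declines: about 0.81 to 0.91 for Group B, and about 1.22 for better-prognosis refusals in Group A. Refusal rate, split by arm and prognosis are all assumptions. The point merits a change because the correction is cheap and progression not recorded at the time may be hard to reconstruct.

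**What to change.** - **Protocol 9.0:** extend the quarterly contact for randomised-untreated subjects to record the date of progression and obtain reports of routine-care scans. No study scans are added.
- **Protocol 16.4.3 and SAP 8.1.3:** add a PFS analysis that counts documented progression or death regardless of the treatment taken.
- **Third sensitivity analysis:** use the documented progression date where one exists, and never date an event before randomisation.
- **Reporting:** give the number of randomised-untreated subjects by arm.

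The cost is a few extra fields at a contact already planned, one more analysis and one line in the disposition table. Routine scans are irregular, some subjects will refuse, and missingness may itself differ by arm. Primary PFS under 16.2 is unchanged, so the bias can be checked but is not removed.
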